### ***13.2.3 Safety analysis***

Safety Set (SS) for safety analysis includes all the subjects having received at least one dose of treatment.

Adverse events should be listed, and the  $\chi^2$  test or the Fisher's exact test is used for analyzing the incidence between two groups.

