### **5. Numbers of Cases & Allocation**

According to the statistical sample size, we are planning to enroll 1000 cases in our study, 500 cases in each group.

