### **13.1 Sample size**

We estimated 918 individuals for recruitment after calculation on the basis of an expected CRA recurrence rate of 21% (30% reduction) for the intervention group and 30% for the placebo group. This study sample size was decided to provide power of 80% at a statistical significance level of 0.05, allowing a 20% dropout rate.

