### 13.2.2 Efficacy analysis

The trial results are evaluated by FAS and Per Protocol Set (PPS). FAS is mainly used to compare the treatment effect for the primary endpoint, and regarding the statistical results from PPS as supplementary analysis. If the subjects have not completed all the treatment, the last exam result will be treated as last observation carried forward (LOCF). Risk ratios (RR) and 95% confidence intervals (CI) are used as the efficacy indicator, comparing by Mantel-Haenszel  $\chi^2$  test methods between the two groups.

Unconditional logistic regression is conducted to compute the odds ratio to estimate the relation between BBR intervention and recurrence of A-CRA and non A-CRA (NA-CRA). Kaplan-Meier method is conducted to estimate progression-free survival of no recurrence of adenoma with log-rank test to compare the survival curve between BBR and placebo group. Survival Curve is used to illustrate time to recurrence of adenoma and RRs are illustrated by Forest plots. We perform predefined subgroup analyses of the primary outcomes to assess BBR effect in terms of age, gender, smoking status, BMI, family history of CRC, number of adenoma and history of CRA.

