### ***13.2.4 Statistical significance***

A two-sided  $P$  value of less than 0.05 is considered to indicate statistical significance.

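### Adverse events are compared between arms only by a significance test, so a non-significant result will not show how large a harm remains possible

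*Combined protocol and SAP*

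**What the plan says.** Section 13.2.3 defines the Safety Set, which "includes all the subjects having received at least one dose of treatment", and then the comparison: "Adverse events should be listed, and the $\chi^2$ test or the Fisher's exact test is used for analyzing the incidence between two groups". It names no risk difference, risk ratio, confidence interval or upper bound.

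Section 13.2.4 gives the only criterion for reading a test: a two-sided P "value of less than 0.05 is considered to indicate statistical significance". It is not restricted to efficacy.

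For efficacy the plan goes further. In 13.2.2, "Risk ratios (RR) and 95% confidence intervals (CI) are used as the efficacy indicator".

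The sample size in 13.1 rests on the primary endpoint alone, with an "expected CRA recurrence rate of 21% (30% reduction) for the intervention group and 30% for the placebo group". No adverse event rate, size of harm worth detecting, or power for safety appears anywhere in the documents.

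**The concern.** A test answers whether the arms differ by more than chance at the 5% level. When events are few, a non-significant answer fits both no excess and a substantial excess, and only an interval tells these apart. The plan provides that interval for benefit and not for harm.

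The setting makes this more than a matter of style. Treatment is preventive and, under section 6.3, continues until the last enrolled participant has two years of follow-up. It is given to people whose adenomas have already been removed. The protocol also treats constipation as a foreseeable problem: the severe form is an exclusion in 4.2 and is provided for in 6.4 as something that may follow the study pills. A reader who wants to weigh a modest excess of such events against fewer recurrences needs both on the same scale, with their uncertainty.

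**Working it through.** **Inputs from the documents.** Section 5 states: "we are planning to enroll 1000 cases in our study, 500 cases in each group". Section 13.1 states: "We estimated 918 individuals for recruitment after calculation", that is 459 per arm. The test and level come from 13.2.3 and 13.2.4. Because the Safety Set needs only one dose, the 20% dropout allowance need not shrink it, so 500 per arm is a fair and favourable figure.

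**Reproducing the plan's own figure.** For p1 = 0.30, p2 = 0.21 and mean 0.255, with two-sided 0.05 and 80% power:

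n = [1.96·√(2·0.255·0.745) + 0.8416·√(0.30·0.70 + 0.21·0.79)]² / 0.09² = 367 per arm, 734 in total.

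734 / (1 - 0.20) = 917.5, rounded up to 918. The stated figure is right. It concerns efficacy only.

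**Power for harms (rates assumed).** The documents give no rates, so a range is used. All pairs of counts from two independent binomials were enumerated at 500 per arm. Each pair was tested by Pearson chi-square when the smaller expected count was at least 5 and by Fisher's test otherwise. That choice rule is the usual convention and is an assumption, because 13.2.3 does not say when each test applies. The last column uses Fisher throughout.

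| Placebo v berberine | Power | Non-significant (1 - power) | Power, Fisher throughout |
|---|---|---|---|
| 0.5% v 1% | 8% | 92% | 7% |
| 1% v 2% | 24% | 76% | 18% |
| 2% v 4% | 46% | 54% | 40% |
| 3% v 6% | 64% | 36% | 58% |
| 1% v 3% | 64% | 36% | 56% |
| 1% v 4% | 89% | 11% | 85% |
| 5% v 10% | 86% | 14% | 83% |

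The first four rows are doublings, and the balance tips between placebo rates of 2% and 3%. The normal approximation agrees: from 2% on placebo, 50% power is reached at 4.1%, just above a doubling. At 459 per arm power is slightly lower (1% v 2%: 21.5%; 2% v 4%: 43%).

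**What an interval would add.** Take 10 events in 500 on berberine and 5 in 500 on placebo.

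- Chi-square: pooled rate 15/1000 = 0.015; (0.010)² / (0.015·0.985·2/500) = 1.69, P = 0.19. Fisher: P = 0.30. Both are non-significant.
- Wilson limits: 1.09% to 3.64% for 10/500 and 0.43% to 2.32% for 5/500.
- Newcombe interval for the difference of 1.0 point: lower 1.0 - √[(2.00 - 1.09)² + (2.32 - 1.00)²] = -0.6; upper 1.0 + √[(3.64 - 2.00)² + (1.00 - 0.43)²] = +2.7 points.
- Risk ratio 2.0: score 95% interval 0.72 to 5.56 (log method 0.69 to 5.81).

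The P value says only that significance was not reached. The intervals say that a small reduction and a more than fivefold increase both remain compatible with the data.

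**The case against.** Four things can fairly be said for the plan.

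First, a reader might infer that any relevant harm of berberine would usually be missed. The documents do not support this. They state neither event rates nor a relevant harm, and the table shows that 1% v 4% and 5% v 10% are detected in well over 80% of trials; 10% v 20% would be detected in about 99% (normal approximation). Only the narrower statement about doublings of uncommon events stands.

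Second, a reader might infer that P above 0.05 will be reported as no difference or as proof of safety. The plan says no such thing. Section 13.2.4 defines what counts as significant and is silent on what a non-significant result means.

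Third, it would be wrong to say that the plan yields nothing but P values on safety. Adverse events are to be listed, and comparing incidence implies counts per arm on a defined denominator. Sections 12.2 to 12.4 add individual recording, serious event reporting and causality grading. A reader given the counts could compute an interval. This stands, but it leaves the summary of harm to the reader while the plan specifies it for benefit.

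Fourth, low power comes from sample size and event rate, so adding an interval would not change any miss rate in the table. That is correct. The miss rates show why a non-significant result is weak evidence; they do not measure a loss caused by the missing interval.

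**Conclusion.** The point holds in a limited form. The planned between-arm safety inference is a test alone, read at two-sided 0.05, while efficacy gets an estimate and an interval. With 500 per arm, a doubling from a placebo rate of about 2% or less would be non-significant in roughly 54% to 92% of trials over the assumed rates of 0.5% to 2%. From about 3% upward a doubling is detected more often than not. These figures rest on assumed event rates, independent binomial counts, full enrolment into the Safety Set and the conventional choice between the two tests.

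Nothing here affects the efficacy result, the sample size or trial conduct. The change is worth making because it is specific, nearly free, and bears directly on how benefit and harm can be weighed. No acceptable margin for harm is stated in the documents and none is implied here, so the intervals are for description and not for a pass or fail rule.

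**What to change.** In 13.2.3, make estimation the basis of the safety comparison. For any adverse event, any serious adverse event, discontinuation due to an adverse event, and constipation where recorded as an adverse event, report the number and percentage per arm in the Safety Set, the risk difference with a Newcombe or score 95% interval, and the risk ratio with a 95% interval. The qualifier on constipation is needed because the symptom list in 7.2.1 does not name it.

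In 13.2.2, add the absolute risk difference with a 95% interval for the primary endpoint. Only a risk ratio is planned there now, and without the difference benefit and harm are not on one scale.

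State in 13.2.3 that P ≥ 0.05 is not evidence of no harm, and keep the chi-square or Fisher P values as descriptive output.

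The cost is a few sentences in the analysis plan, a somewhat longer safety table and one extra efficacy line. No participants or procedures are added. The downside is that intervals for rare events will be wide.

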### ***13.2.4 Statistical significance***

A two-sided  $P$  value of less than 0.05 is considered to indicate statistical significance.

### ***13.2.5 Statistical software***

Statistical analyses are conducted with the use of SAS software, version 9.4 (SAS Institute Inc., Cary, NC, USA).

## **14. Data Management**

Establish the procedure for data storage, transfer, and query. The archived documents include: the participant's CRF, subject code form, serious adverse event report form, completed GCP form, follow-up report form and related original medical documents. The transferred data include: the subject random table, CRF, serious adverse event report form, and the documents required for summary. The main investigator at each center has the right to inspect the relevant trial data and original records.

A secure electronic database (Bo Shi, China) that conformed to GCP requirements is used for data management. A timely training of personnel has been conducted before electronic data input, and access to the corresponding system rights has been granted. The investigator of each center can only reach their own data page by using a specific account and pass code, and the principal investigator in Ren-Ji Hospital can view and centralize all the baseline and follow-up information of participants, yet with no permission to modify the data of other centers.

It is necessary to adopt standardized statistical methods and invite familiar biostatistician to summarize and analyze the results.

To ensure the reliability and completeness of the trial data, the principle investigator

has the responsibility to monitor systematically the data of each center at regular intervals, and evaluate whether the execution is consistent with the protocol and whether the reported data are consistent with the records of each center. A report should be prepared for each visit.

## **15. Quality Control**

Standard operating procedure (SOP) should be used at all study centers for quality control.

In order to ensure the quality of the multi-center trial, the main investigators should discuss together and develop a comprehensive clinical research plan before the start of the formal trial. The medical personal participating in the trial should also receive GCP training.

All observed results and abnormal finding in the clinical trial should be cautiously verified and recorded in time to ensure data reliability. All kinds of instruments, equipment, reagents and standards used in various examination items in the clinical trial should have strict quality standards, and we should make sure that they works properly. Data record and transfer must be performed by an experienced physician and checked by a special person to ensure data scientificity and accuracy. The conclusions of the clinical trial must be based on the original data.

The personal in charge should write CRFs in a complete, detailed and accurate manner. The CRFs should be completed as soon as possible after the examinations, and reported or preserved according to the procedure after been signed by the main investigator of each center. All data related to the trial should be centrally managed and analyzed.

## **16. Ethics**

The trial will be carried out in accordance with the Chinese Guideline for Good Clinical Practice (GCP) and the principles laid down in the Declaration of Helsinki. The trial will not be initiated before the protocol has been approved by Institutional Review Board (IRB) of the clinical research center.

The study personal has the responsibility to provide a complete and comprehensive introduction in writing of the study purpose, procedure and potential risk to each participant or his representative before enrollment, and let the participant know that he/she has the right to withdraw from the study at any time. An informed consent form must be given to each patient prior to enrollment, and the study personal should retrieve the signed consent before the patient enters the study.

## **17. Follow-up & Medical Measures After the Trial**

If adverse events persist after discontinuation of the study drugs, the patients should be followed and receive reasonable treatment until clinical recovery or their conditions have been stabilized with corresponding records on the CRFs. If the participant suffers from health damage due to adverse drug reactions, he/she will receive appropriate medical compensation given by sponsor.

## **SUMMARY OF PROTOCOL CHANGES**

### **Protocol Changes Version 1.0 (July 16, 2014) to 1.1 (Nov. 20, 2014):**

- 1) Cover page: Participating centers

#### ***Addition of the following:***

The Affiliated Drum Tower of Nanjing University Medical School

#### ***Deletion of the following:***

Zhongshan Hospital, Fudan University

## **Protocol Changes Version 1.1 (Nov. 20, 2014) to 1.2 (Dec. 20, 2014):**

### **1) Section 4. Selection of Trial Population:**

***Addition of the following:***

#### **4.1 Inclusion criteria**

1. Individuals aged 18-75 years
2. Individuals who had at least one and no more than 6 histologically confirmed CRAs removed within 6 months before recruitment
3. Individuals who are able to swallow pills
4. Individuals who voluntarily sign the consent form after being fully informed and understanding the purpose and procedure of this study, characters of the disease, effect of medication, methods of related examinations, and potential risk/benefits of the study

#### **4.2 Exclusion criteria**

1. Individuals whose adenoma was not completely removed during previous colonoscopy
2. Individuals with a history of familial adenomatous polyposis (FAP) or hereditary non-polyposis colorectal cancer (HNPCC, Lynch syndrome)
3. Individuals who are taking regularly aspirin, nonsteroidal anti-inflammatory drugs (NSAIDs), cyclo-oxygenase 2 (COX2) inhibitors, calcium or vitamin D
4. Individuals with a history of subtotal/total gastrectomy or partial bowel resection
5. Individuals who are intolerant to another colonoscopy examination
6. Individuals who are hypersensitive or intolerant to the drugs
7. Individuals with severe heart, liver or kidney disease, or any cancer history
8. Individuals presenting severe constipation
9. Pregnant women, women during breast-feeding period, or women with expect pregnancy
10. Individuals with mental diseases who are not able to cooperate
11. Individuals who are involved in designing, planning or performing this trial

***Deletion of the following:***

**4.1 Inclusion criteria**

1. Individuals aged 18-70 years, without gender limitation
2. Individuals who had at least one and no more than 6 histologically confirmed CRAs removed by EMR, ESD or APC within 1 month
3. Excluding individuals with familial adenomatous polyposis (FAP) by asking medical and family history
4. Individuals who voluntarily sign the consent form

**4.2 Exclusion criteria**

1. Individuals suffering from other malignancy at the same time
2. Individuals with other severe diseases and the expected survival is less than 3 years
3. Individuals who are intolerant to another colonoscopy examination
4. Pregnant women, women during breast-feeding period, or women with expect pregnancy
5. Individuals with a history of subtotal/total gastrectomy or partial bowel resection
6. Individuals presenting severe constipation
7. Individuals who are taking regularly aspirin, cyclo-oxygenase 2 (COX2) inhibitors or calcium
8. Individuals with mental diseases who are not able to cooperate
9. Individuals who are involved in designing, planning or performing this trial
10. Individuals who are hypersensitive or intolerant to the drugs
11. The investigators think that the subject is not suitable for inclusion

## 2) Section 6.2 Dose & usage

### ***Addition of the following:***

BBR hydrochloride 300mg Bid×36 months

Placebo 3# Bid×36 months

### ***Deletion of the following:***

BBR hydrochloride 300mg Tid×36 months

Placebo 3# Tid×36 months

## Protocol Changes

### Version 1.2 (Dec. 20, 2014) to Final Version (Dec. 22, 2018):

- 1) Cover page: Participating centers

#### *Addition of the following:*

The Seventh Medical Center of PLA General Hospital

#### *Deletion of the following:*

PLA Army General Hospital

- The Renaming Declarations of PLA Army General Hospital have been filed for reference and approved by IRB of the leading center.

## 2) Section 1

### *Addition of the following:*

#### **1. Background**

Colorectal cancer (CRC) is a leading cause of cancer deaths worldwide and in recent years its incidence is increasing rapidly in China, which constitutes a major public health burden [1]. Almost 90% of CRC cases develop from precursor adenomatous polyps, through a series of genetic changes known as adenoma-carcinoma sequence during at least 10 years [2]. Detection and removal of colorectal adenoma (CRA) could reduce CRC mortality risk by colonoscopy [3], but the recurrence rate is high [4]. Chemoprevention of adenoma and cancer remains its importance in both aspects of public health and cost effectiveness.

Our previous clinical trial has shown that supplementation of 1mg folic acid per day decreases significantly incidence of sporadic CRA in elder healthy people [5]. However, the role of folic acid in the prevention for CRA recurrence has kept controversial to date [6]. Favorable effects of several kinds of medicine on the secondary prevention of CRA have been reported in observational studies and randomized controlled trials (RCTs), including aspirin, vitamin D, etc. A latest meta-analysis summarized that regular intake of aspirin or COX-2 inhibitors seemed to be effective in preventing relapse of adenomas, but meanwhile a dose-related increase of gastrointestinal complications could be observed [7]. To evaluate the protective potential of vitamin D3 and/or calcium, a large-scale randomized trial conducted in 2259 participants with a recent history of CRA showed unfortunately no significant effect of any group [8]. Thus looking for suitable prophylactic drugs for CRA recurrence is urgent needed.

Berberine (BBR) hydrochloride, a natural isoquinoline alkaloid extracted from the Chinese herb *Coptis chinensis*, has been widely used in China to cure diarrhea and enteritis for centuries with minimal side effects [9], and accumulating evidences have showed its anticancer activity, but its molecular mechanism has not been quite clear. Our previous study presented that BBR could block the colorectal adenoma-carcinoma sequence in mice by changing microbiota structures [10]. In order to further evaluate

its clinical potential for CRA recurrence, we have initiated this clinical trial of pharmacological intervention in persons after a recent polypectomy.

***Deletion of the following:***

**1. Title**

A randomized, placebo-controlled, multicenter, prospective clinical study of Berberine (BBR) hydrochloride in preventing recurrence and carcinogenesis after endoscopic removal of colorectal adenomas (CRAs)

### 3) Section 6 Interventions

*Addition of the following:*

## 6. Interventions

### 6.1 Medication

#### 6.1.1 Drug1

- Ingredient: BBR hydrochloride
- Dosage form: Tablet

#### 6.1.2 Drug 2

- Ingredient: Placebo
- Dosage form: Tablet

All the study pills are provided by Shanghai SINE Pharmaceutical Co., Ltd.

### 6.2 Dose & usage

BBR hydrochloride 300mg Bid

Placebo 3# Bid

### 6.3 Duration

Until the last enrolled patient reached the 2-years follow-up.

### 6.4 Concomitant treatment

Conventional symptomatic treatment can be used in both group during the study period. When severe constipation occurs in participants after taking study pills, they are allowed to take one prokinetic drug within 2 weeks.

### 6.5 Participant timeline

The time schedule of enrollment, interventions and visits for participants is shown in a schematic diagram (Table 1) following the instructions in the SPIRIT 2013 (Standard Protocol Items: Recommendations for Interventional Trials) statement [11].

Table1: Participant timeline

|                                    | Study Period |        |                 |    |    |    |    |    |    |    |                           |
|------------------------------------|--------------|--------|-----------------|----|----|----|----|----|----|----|---------------------------|
|                                    | Allocati     | Run-in | Post-allocation |    |    |    |    |    |    |    | Closeout                  |
| Time points                        | 0            | -2wks  | M3              | M6 | M9 | 12 | 15 | 18 | 21 | 24 | M24-M36
Final visit    |
| Enrollment:                 |              |        |                 |    |    |    |    |    |    |    |                           |
| Eligibility screen                 | X            |        |                 |    |    |    |    |    |    |    |                           |
| Informed consent                   | X            |        |                 |    |    |    |    |    |    |    |                           |
| Interventions:              |              |        |                 |    |    |    |    |    |    |    |                           |
| BBR
hydrochloride or
placebo |              |        | ◆               |    |    |    |    |    |    | ◆  | Return
unused
pills |
| Assessments:                |              |        |                 |    |    |    |    |    |    |    |                           |
| Demographics                       | X            |        |                 |    |    |    |    |    |    |    |                           |
| Smoking status                     | X            |        |                 |    |    |    |    |    |    |    |                           |
| Height                             | X            |        |                 |    |    | X  |    |    |    | X  |                           |
| Weight                             | X            |        |                 |    |    | X  |    |    |    | X  |                           |
| Medical history                    | X            |        |                 |    |    |    |    |    |    |    |                           |
| Family history                     | X            |        |                 |    |    |    |    |    |    |    |                           |
| Manifestations                     | X            |        | ◆               |    |    |    |    |    |    | ◆  |                           |
| Laboratory tests                   | X            |        |                 |    |    | X  |    |    |    | X  |                           |
| Colonoscopy                        | X            |        |                 |    |    | X  |    |    |    | X  |                           |
| Histology                          | X            |        |                 |    |    | X  |    |    |    | X  |                           |
| Stool samples                      | X            |        |                 |    |    | X  |    |    |    | X  |                           |
| Drug distribution                  |              | ◆      |                 |    |    |    |    |    |    | ◆  |                           |
| Adverse event                      | X            |        | ◆               |    |    |    |    |    |    | ◆  |                           |
| Medication                         |              | ◆      |                 |    |    |    |    |    |    | ◆  |                           |

